3.7 Data Analysis

3.7.1 General Analytic Approach for Aim 1:

Aim 1: To compare the effects of the intervention (DSME+ Mind-STRIDE) with those of usual care (DSME-alone) on diabetes distress, diabetes self-efficacy, and DSM in military Veterans over time.

Hypotheses. From baseline to 24-week post-intervention, DSME+ Mind-STRIDE compared to DSME-Alone will:

1. Significantly reduce DRD (primary outcome)
2. Significantly increase mindfulness, diabetes self-efficacy and diabetes self-management (secondary behavioral outcomes)
3. Significantly decrease HbA1c (distal metabolic outcome)

Independent variable: The Mind-STRIDE intervention, which includes mindfulness stress reduction, mindfulness meditation training and home practice.

Dependent variables: The primary outcome on which the analysis is powered is DRD measured by the PAID scale. Secondary outcomes include diabetes self-efficacy, diabetes self-management, mindfulness, and glycemic control, measured by HbA1c.

Analysis: To assess whether there are group differences over time, we will use separate linear (or non-linear depending on outcome) mixed models for each outcome (diabetes distress, primary), diabetes self-efficacy, diabetes self-management, mindfulness and glycemic control (secondary) for 3 time points (baseline, 12 weeks post-intervention, and 24 weeks post-intervention). The base model will include fixed effects for treatment group DSME+ Mind-STRIDE, DSME-Alone group, time, and the interaction between treatment group and time. To the extent possible, post-hoc analyses to explore the possible relationships between mindfulness and diabetes-related distress (as well as the interaction between them) on the distal secondary outcome, glycemic control will be performed.

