Power analysis: Power calculations for Aim 1, hypothesis 1 of this study were based on a repeated measures design (2 sided $\alpha = .05$) with 2 treatment groups (DSME+ Mind-STRIDE; DSME-Alone) and 3 time points (baseline, 12 weeks post intervention, 24 weeks post-intervention). We computed sample size estimates that were powered to detect an overall treatment group difference in DRD (PAID scale score) as well as a treatment group difference over time (interaction between treatment group and time). Based on our pilot work, a medium effect size ($d = .6$) gives a clinically meaningful change in PAID score. Using a medium ($d = .5$) effect size, and estimates of the correlations between observations on the same subject of $r = .5$, powering at 80% gives a sample size estimate of 86 (~43 per group). To account for possible clustering due to the randomization occurring in groups of $n = 5$ participants, the required total sample size (86) was inflated by a factor of $(1 + (5-1) * p)$, where p is the intra-cluster correlation coefficient.^{78, 79} A conservative estimate of the intra-cluster correlation of $p = 0.05$, gives an increased sample size of 104 (~52 per group). To ensure a sample of 104 at study completion, 126 Veterans will need to be recruited over the 2-year study period. This number of 126 Veterans is approximately 20% of the usual number of Veterans referred for DSME over two years and is within what is considered reasonable to recruit based on our pilot data. Sample size estimates were computed in Stata Statistical Software: Release 12 (College Station, TX: StataCorp LP; 2011).

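### The sample size of 86 (104 after clustering) fits a group main effect that averages in baseline; the baseline-to-week-24 comparison has about 64% power at d = 0.5, not 80%

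*Combined protocol and SAP*

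**What the plan says.** All of this is in section 3.7.1 of the combined protocol and SAP.

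- **Hypothesis.** The primary hypothesis on diabetes-related distress (PAID) is framed as "From baseline to 24-week post-intervention, DSME+ Mind-STRIDE compared to DSME-Alone will" reduce it.
- **Model.** Each outcome gets a mixed model with group, time and group-by-time terms, and baseline is one of the three outcome visits.
- **Power inputs.** The calculation is for a "repeated measures design (2 sided $\alpha = .05$) with 2 treatment groups" and "3 time points (baseline, 12 weeks post intervention, 24 weeks post-intervention". The within-subject correlation is 0.5. The pilot is cited to the effect that "a medium effect size ($d = .6$) gives a clinically meaningful change in PAID score", but the sizing is done "Using a medium ($d = .5$) effect size".
- **Effects covered.** The estimates are said to be "powered to detect an overall treatment group difference in DRD (PAID scale score) as well as a treatment group difference over time", the latter being the interaction.
- **Result.** "powering at 80% gives a sample size estimate of 86 (~43 per group". A design effect of 1.2 (groups of 5, intra-cluster correlation 0.05) raises this to 104 completers, and 126 are to be recruited to allow for attrition.

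The section does not name the test that produced 86, the SD to which d refers for the interaction, or the contrast that decides hypothesis 1.

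**The concern.** A main effect averaged over three visits and a change from baseline to week 24 are different estimands with different variances, so one sample size gives them different power. The main effect is also a poor target in a randomised trial when baseline is one of the averaged visits. Any treatment effect is diluted by a visit at which the expected difference is zero.

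If 86 came from that main effect, the 80% does not carry over to the hypothesis the trial will test. This is the only power statement for the primary outcome. A non-significant result would be read as coming from a trial with a 20% chance of missing the planned effect, when the chance is nearer 36%.

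**Working it through.** **Inputs (section 3.7.1).** d = 0.5 in units of the single-visit SD; r = 0.5 between any two visits; three visits; two-sided alpha 0.05; power 80%; 1:1 allocation; design effect 1 + (5 − 1) × 0.05 = 1.2.

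**Formula.** With v the variance of the contrast for one patient, in units of the single-visit variance:

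n per group = 2 × (1.960 + 0.842)² × v / d²

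**Step 1: reproduce 86.** For the mean of three visits, v = (1 + 2r)/3 = 0.667, so n = 2 × 7.85 × 0.667 / 0.25 = 41.9, or 42 per group (84 in total) by the normal approximation. With the noncentral t (equivalently F) distribution, power is 0.792 at 42 per group and 0.801 at 43. The smallest adequate total is therefore exactly 86. Then 86 × 1.2 = 103.2, rounded up to 104 as in the plan.

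**Step 2: try other contrasts at d = 0.5.**

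| Contrast | v | Total N for 80% (normal / t) | Power at 43 per group (normal / t) |
|---|---|---|---|
| Mean of 3 visits, 0.5 SD at every visit | (1 + 2r)/3 = 0.667 | 84 / 86 | 81.0% / 80.1% |
| Mean of weeks 12 and 24, unadjusted | (1 + r)/2 = 0.75 | 96 / 98 | 76.3% / 75.4% |
| Mean of weeks 12 and 24 minus baseline | (1 + r)/2 + 1 − 2r = 0.75 | 96 / 98 | 76.3% / 75.4% |
| Week 24 adjusted for baseline (ANCOVA) | 1 − r² = 0.75 | 96 / 98 | 76.3% / 75.4% |
| Mean of weeks 12 and 24 adjusted for baseline | (1 + r)/2 − r² = 0.50 | 64 / 66 | 90.6% / 90.0% |
| Change from baseline to week 24 | 2(1 − r) = 1.0 | 126 / 128 | 64.0% / 63.0% |
| Week 24 alone, unadjusted | 1.0 | 126 / 128 | 64.0% / 63.0% |

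Only the first row gives 86.

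**Step 3: what the first row assumes.** With a baseline difference of zero, an average of 0.5 SD over three visits needs 0.5 × 3/2 = 0.75 SD at both follow-ups. If the follow-up differences are 0.5 SD, the average is (0 + 0.5 + 0.5)/3 = 0.333 SD, and power for the main effect at 43 per group is 47% (t: 46%).

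**Step 4: the hypothesised contrast.** In the planned model with complete data, the week-24 group-by-time contrast equals the difference in mean change.

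- At 43 per group, 0.5 / √(2 × 1.0/43) = 2.318, and the normal-approximation power is Φ(2.318 − 1.960) = 64%.
- With 104 completers, the effective total is 104/1.2 = 86.7 and power is 64.3%.
- For 80% power, n = 2 × 7.85 × 1.0 / 0.25 = 62.8, or 63 per group (126 in total; 128 by t). After clustering, 126 × 1.2 = 151.2, or 152 completers. At the plan's own retention of 104/126, that is about 184 recruited.
- At the planned size, the difference detectable with 80% power is 0.60 SD (t: 0.61). Baseline adjustment at week 24 brings it to 0.52 (t: 0.53).

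**Step 5: the interaction.** The joint 2-df test at 43 per group has noncentrality (43/2) × Σ(δ − mean δ)² / (1 − r). For differences (0, 0.5, 0.5) this is 21.5 × 0.1667 / 0.5 = 7.17, giving 66% power by F and 67% by chi-square. For (0, 0.25, 0.5) it is 5.375, giving 53%.

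**Sensitivity to r.** With d on the single-visit SD, the change contrast has 50% power at r = 0.3, 74% at r = 0.6 and 85% at r = 0.7. At r = 0.5 the SD of change equals the single-visit SD, so 64% holds whichever of the two d refers to.

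**The case against.** **The source of 86 is inferred.** The plan names no test, and the simple normal formula gives 84. This is true. However, the t/F version returns exactly 86, and none of the six other contrasts does. The power of the week-24 contrast also does not depend on where 86 came from.

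**Week-24 change is only one reading.** The section gives the period for the hypothesis but no single contrast or degrees of freedom, and the change score is among the least efficient choices. The mean of both follow-ups minus baseline, or week 24 adjusted for baseline, has about 76%. That widens the range but still falls short of 80%. A baseline-adjusted average of both follow-ups would reach 90%, but the plan does not specify that analysis.

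**The interaction claim may hold under a convention.** With the generic effect size f = 0.25, the interaction needs only about 28 patients, which may explain the claim of power for both effects. That f is not a 0.5 SD difference at week 24, and the plan does not define d for the interaction.

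**The plan calls d = 0.6 clinically meaningful.** At that effect the change contrast has 79 to 80% power and the baseline-adjusted week-24 contrast about 89%. This stands, and it makes an honest restatement possible. But the plan attached its 80% to d = 0.5.

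**The clustering allowance is called conservative.** With no clustering, 52 per group gives 71 to 72% for the change contrast and about 83% with baseline adjustment. The change contrast in the model as written still misses 80%.

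**Conclusion.** The concern holds. With the plan's inputs and its model as written, 80% power at a post-baseline difference of 0.5 SD is reached neither for the overall group effect (46 to 47%) nor for the interaction (66 to 67%). It is not reached for the hypothesised week-24 change either (63 to 64%). The completers needed for that last contrast are 126 before clustering and 152 after it, against 86 and 104 in the plan. The plan's recruitment figure of 126 is 104 completers inflated for attrition; its match with the 126 needed before clustering is a coincidence.

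These figures rest on r = 0.5 between all pairs of visits, d on the single-visit SD, complete data on 104 patients and a design effect of 1.2. That 86 is a main-effect figure is an inference from exact reproduction.

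**What to change.** Keep recruitment at 126 and rewrite the power paragraph around the contrast that decides hypothesis 1. Name that contrast and state the SD to which d refers. Suggested text:

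> Hypothesis 1 is tested by the between-group difference in PAID change from baseline to week 24. With 104 completers, a design effect of 1.2 and a within-subject correlation of 0.5, power is about 64% for a difference of 0.5 SD and about 80% for 0.60 SD (normal approximation; 63% and 79% with the t distribution).

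Remove the statement that 86 gives 80% for both the overall difference and the interaction. If a baseline-constrained or ANCOVA-type week-24 analysis is adopted as primary, the paragraph can instead give about 76% for 0.5 SD; that figure should not appear unless the model section specifies the analysis.

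The cost is wording. No patients or procedures are added, but the stated power at d = 0.5 becomes less favourable. Because the plan already treats d = 0.6 as clinically meaningful, power of about 80% at that effect can still be stated.

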[name] PhD, Associate Professor of Biostatistics at the University of Pittsburgh Graduate School of Public Health, will oversee statistical analysis for Aim 1. Analyses for Aim 1 will be performed using Stata statistical software. Diabetes distress (the primary outcome) and secondary outcomes (mindfulness diabetes self-efficacy, diabetes self-management, and HbA1c) will be assessed for normality and appropriate data transformations will be used if necessary. Descriptive statistics will be computed to determine central tendency, data sparseness, and existence of outliers for all other continuous variables. Frequency distributions will be generated for categorical variables to identify data sparseness, and categories with small frequencies will be merged when appropriate. In addition, we will consider categorization of continuous predictors if the distributions are skewed or violate assumptions of linearity. Differences in covariates by treatment group will be tested using chi-square (or Fisher's exact) statistics for categorical variables and t-test (or Mann-Whitney) for continuous variables. Graphical procedures will be used to assess simple change in the outcomes over time. For the main analyses for Aim 1, we will test study hypotheses by using linear mixed models (or non-linear

mixed models where appropriate), which account for repeated measures and assess change over time (baseline, 12 weeks, 24 weeks). The linear mixed model allows for missing data if data are missing at random. Demographic variables with a univariate association with the outcome ($p < 0.10$) or differed by treatment group at baseline ($p < 0.05$) will be considered for inclusion in a multivariate model. Covariates will be retained in the final multivariable models if significant at $p < 0.05$. All tests will be two-sided. All analyses will be conducted as intent-to-treat analyses and include all patients in the groups to which they were randomized, regardless of adherence and/or subsequent withdrawal.

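### Covariates for the Aim 1 models are chosen by p-value, and the plan does not fix which model or which contrast decides hypothesis 1

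*Combined protocol and SAP*

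**What the plan says.** All places are in the combined protocol and SAP.

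- **Section 3.7.1, Analysis.** "The base model will include fixed effects for treatment group", time and their interaction. No covariates are listed.
- **Section 3.7.1, description of the main analyses.** Variables become candidates in two ways. One is by outcome screening: "Demographic variables with a univariate association with the outcome" at p < 0.10. The other is by a baseline difference between arms at p < 0.05. Qualifying variables are to be considered, and then "Covariates will be retained in the final multivariable models if significant at" p < 0.05.
- **Section 3.7.1, Power analysis.** The sample size is said to cover both an overall group difference in PAID score and a group-by-time difference.
- **Section 3.7.1, Missing Data.** Baseline variables that differ significantly between participants with and without complete outcome data are added to the model.
- **Section 3.9.** Medication changes during the study are to be controlled for in the analysis.

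Nowhere is it stated whether the base model or the final multivariable model gives the test of hypothesis 1, or which of the two powered effects is decisive.

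**The concern.** In a randomised trial a baseline difference between arms is due to chance, so a significance test of it is no reason to adjust. Keeping covariates because they predict the outcome in this sample, and then quoting the ordinary standard error, treats the chosen model as if it had been fixed beforehand. That standard error can be too small.

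The larger issue is that two models and two contrasts remain open for the primary outcome. If either model can be reported, there is a second route to a significant result. At stake is whether the primary test has the stated 5% error rate and is uniquely defined.

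**Working it through.** **1. Inputs from the plan (Section 3.7.1, Power analysis).** Two-sided α = 0.05; "Using a medium ($d = .5$) effect size"; r = 0.5; "3 time points (baseline, 12 weeks post intervention, 24 weeks post-intervention"); 80% power. Cluster size is 5 and the intra-cluster correlation 0.05. The plan expects 104 completers from 126 recruited, an implied dropout of 1 − 104/126 = 17.5%.

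**2. Reproducing the plan's figure.** The plan states "powering at 80% gives a sample size estimate of 86 (~43 per group").
- Variance factor for the mean of three measurements: (1 + 2 × 0.5)/3 = 2/3.
- Normal formula, per group: 2 × (1.960 + 0.842)² × (2/3) / 0.5² = 41.9, so 42 per group or 84 in total.
- Noncentral t: 43 per group, 86 in total, power 80.1%.
- Design effect: 1 + 4 × 0.05 = 1.2, and 86 × 1.2 = 103.2, stated as 104.

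So the stated size reproduces from the overall, time-averaged group effect.

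**3. Assumptions for the simulation.** The demographic questionnaire in Section 3.6.1 lists 10 items. I take 10 candidates, or 17 if the other potential covariates are screened too. Covariates are independent and normal. Either none is prognostic, or three together explain R² = 0.15 of the variance of one measurement. There is no clustering. The rule is applied mechanically: entry at p < 0.10 with the outcome or p < 0.05 between arms, then backward elimination at p < 0.05.

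**4. Type I error for the overall group effect (no true effect, N = 104, 20,000 replicates per row, Monte Carlo standard error 0.16 points).**

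| Candidates | Prognostic | Base model | Covariates fixed in advance | Stated rule | Either model |
|---|---|---|---|---|---|
| 10 | none | 5.06% | 5.06% | 5.48% | 5.78% |
| 10 | 3 | 5.00% | 5.10% | 5.52% | 7.67% |
| 17 | none | 5.04% | 5.04% | 5.72% | 6.15% |
| 17 | 3 | 5.00% | 4.99% | 5.76% | 7.92% |

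A separate simulation with 10 candidates gave 5.3 to 5.8% under the rule and 6.1 to 6.9% for either model. With 10 non-prognostic candidates the mean model standard error was 0.158 against an empirical SD of 0.162: 1 − 0.158/0.162 = 2.5% too small. The separate simulation gave about 3%.

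**5. The arm-by-time contrast.** With complete data this compares within-person changes, so a covariate that is constant over time and enters as a main effect cancels. Mixed models fitted to 60 simulated trials in each setting confirmed it:
- Complete data: the week-24 estimate was unchanged (difference below 1e-14) and the standard error ratio was 1.000.
- 17.5% dropout: the mean standard error ratio was 0.999 (range 0.991 to 1.003), and estimates moved by at most 0.04 SD.

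A null simulation of the week-24 term (10 candidates, 17.5% dropout, 2,000 replicates, Monte Carlo standard error about 0.5 points) gave these rates for base / selected / either model:
- No prognostic covariates: 6.25 / 6.15 / 6.35%.
- Three prognostic covariates: 6.1 / 6.0 / 6.4%.

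The level above 5% reflects z-tests and Monte Carlo error. The gain from being able to choose a model is 0.1 to 0.3 points.

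**6. What the choice of contrast does to power.** For the change from baseline to week 24, the variance factor is 2 × (1 − 0.5) = 1. At 43 per group the noncentrality is 0.5 × √(43/2) = 2.32, so power is Φ(2.32 − 1.96) = 64%. For 80%, 2 × 7.85 / 0.25 = 62.8, so 63 per group or 126 in total, before the design effect and dropout.

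**The case against.** The strongest reply is that hypothesis 1 is worded as a change from baseline to 24 weeks, so arm by time is the natural test. For that test the selection rule does almost nothing (step 5). This stands. A reader might infer from the rule that the standard error of the primary test is generally understated and its error rate clearly inflated. The documents do not support that for the arm-by-time contrast. It would need selected covariate-by-time terms, which the plan never mentions, or time-varying covariates. The medication adjustment in Section 3.9 could be time-varying, but its form is not given.

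It is also fair that qualifying variables are only to be considered, and that the plan does not call the selected model primary. A reader might infer that it is, but the text leaves this open. Even for the overall effect, the excess from the rule alone is under one percentage point.

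The reply does not close the point. The plan powers the overall difference as well, its sample size reproduces from that contrast, and nothing makes the interaction the sole test. The discretion in considering variables adds a further data-dependent choice.

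**Conclusion.** The point holds as one of pre-specification. The plan states a poor covariate rule and leaves both the model and the contrast for hypothesis 1 undecided. The inflation under the rule alone is small, and the open choice between models is the larger part of the risk on the overall group effect. On the arm-by-time contrast both are negligible if covariates are constant over time and enter as main effects.

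Confidence is high on what the plan says and moderate on the exact error rates, which rest on the assumed number, independence and strength of the covariates and on mechanical use of the rule. The simulations do not count the completer-difference adjustment, the medication adjustment, or the category merging and categorisation of predictors that Section 3.7.1 also allows.

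**What to change.** Amend Section 3.7.1 before any outcome data are seen:

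1. Name one primary model: arm, time, arm by time, and a short list of baseline covariates fixed now and kept whatever their p-values. Candidates already collected include age, diabetes duration, HbA1c and PHQ-9. Diabetes type is in neither the demographic questionnaire nor Table 5, so it would need a stated source. In the HbA1c model, baseline HbA1c is already part of the outcome series and should not also be a covariate.
2. Name one deciding contrast for hypothesis 1, for example arm by time at week 24, and reconcile the power statement with it (step 6).
3. Delete baseline significance testing and p-value retention as criteria.
4. Label every data-selected model a sensitivity analysis. This includes the completer-difference adjustment under Missing Data and the medication adjustment in Section 3.9, which would otherwise contradict a single primary model.

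The cost is SAP wording and a few degrees of freedom, with no new data. Time-constant main-effect covariates will add little precision to an arm-by-time contrast, so the gain there is a uniquely defined test. If week-24 arm by time is chosen, the documented power must be restated.

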Missing Data. We will review all assessments for completeness during the session in which it is collected to attempt to minimize missing data for Aim 1. We will attempt to assess the missing data mechanism for missing data due to lost to follow-up or withdrawal. If there are significant differences in baseline variables between those subjects that have complete outcome data and those that do not, we will adjust for those covariates as part of the modeling.⁸⁰ If no systematic differences are found or if the missing data is intermittent, the missingness will be handled as part of the regression modeling. Using linear mixed linear models allows the use of all available data, including data from those who are missing one or more of the assessments. We will also perform completers only analyses and see if these differ compared to the modeling using all of the available data to assess sensitivity to the missingness.

3.7.2 General Analytic Approach for Aim 2

Aim 2: To identify Veteran satisfaction and experiences with DSME +Mind-STRIDE.

We will use Convergent Parallel Design (Figure 5) to develop a more complete understanding of the research questions by obtaining different but complementary quantitative (Aim 1) and qualitative (Aim 2) data.⁸¹ Collecting and analyzing two independent strands of data at the same time in a single phase will enable us to prioritize the methods equally while keeping the data analysis independent. We will then mix the results at the point of interface, looking for convergence, divergence, contradictions or relationships of the two sources of data that will inform the overall interpretation of study results.

[figure not shown]

Figure 5. Convergent Parallel Design

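### Dropout-related covariates are chosen by an underpowered significance test (22 v 104); a short fixed list would be better, although the likely bias in the treatment effect is small

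*Combined protocol and SAP*

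**What the plan says.** Section 3.7.1 relies on a linear mixed model for three time points and notes that it accommodates data missing at random. The Missing Data paragraph then sets a rule with two branches.

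- Significant: "If there are significant differences in baseline variables between those subjects that have complete outcome data and those that do not", then "we will adjust for those covariates as part of the modeling".
- Not significant: "If no systematic differences are found or if the missing data is intermittent, the missingness will be handled as part of the regression modeling".

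The paragraph names no variables and gives no significance level. Its one sensitivity analysis is this: "We will also perform completers only analyses and see if these differ compared to the modeling using all of the available data".

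A separate covariate rule in section 3.7.1 is limited to one class of variable: "Demographic variables with a univariate association with the outcome ($p < 0.10$) or differed by treatment group at baseline ($p < 0.05$) will be considered". Covariates then stay in the final model only if they reach p < 0.05.

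The number of non-completers is not stated. It follows from the power analysis: "To ensure a sample of 104 at study completion, 126 Veterans will need to be recruited over the 2-year study period".

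**The concern.** Missing at random is a statement about what the model conditions on. If a baseline variable predicts both dropout and later PAID, beyond what the observed PAID scores already carry, it should be in the model or in an imputation step. The plan lets a hypothesis test decide, and reads a non-significant result as the absence of a systematic difference. With about 22 people in the smaller group, a non-significant result says little.

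Depression, post-traumatic stress and social support are plausible predictors of both dropout and distress. All are measured at T1 (Table 5) and listed under Potential Covariates in section 3.6.1. Because the rule fixes neither variables nor level, the content of the primary model would also depend on the observed dropout and on choices made after the data are in.

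**Working it through.** **1. The plan's own figures.** Inputs from the power analysis in section 3.7.1: d = 0.5, r = 0.5, three time points, two-sided 0.05, 80% power, cluster size 5, intra-cluster correlation 0.05.

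- Variance factor for a three-visit mean: (1 + 2 × 0.5)/3 = 0.667. Effective difference: 0.5/√0.667 = 0.612.
- Non-central t power is 79.2% with 42 per arm and 80.1% with 43, so 86 in total, as stated.
- Inflation: 1 + 4 × 0.05 = 1.2; 86 × 1.2 = 103.2, rounded up to 104, as stated.
- Non-completers: 126 − 104 = 22, or 22/126 = 17.5%.

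**2. How often the test misses a real difference.** Two-sample t test, 22 v 104, 124 degrees of freedom, critical value 1.979. The non-centrality is d/√(1/22 + 1/104) = 4.261 × d. Section 3.7.1 states that "All tests will be two-sided"; the 0.05 level is my assumption. The documents give no size for the completer v non-completer difference, so a range is shown.

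| True difference (SD) | Power | Missed |
|---|---|---|
| 0.2 | 14% | 86% |
| 0.3 | 25% | 75% |
| 0.4 | 39% | 61% |
| 0.5 | 56% | 44% |
| 0.8 | 92% | 8% |

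Power of 80% needs a difference of 0.66 SD. A looser screen helps only in part: at 0.5 SD the miss rate is 32% at a level of 0.10 and 20% at 0.20. If participants missing a single visit also count as incomplete, the smaller group grows. With 30 of the 126 incomplete, the miss rate at 0.5 SD is 34%; with 35 it is 30%.

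**3. Which variables depend on this test.**

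- PAID: Table 5 shows it at screening, T2 and T3. The screening value is therefore the baseline of the three-time-point model and is used whatever the test shows.
- Demographic variables, such as age: may enter through the separate covariate rule.
- PHQ-9, PCL-5, social support, comorbidity: no other entry rule is stated.

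**4. What a miss does to the treatment effect.** Assume 17.5% drop out before T2, PAID visits correlate 0.5 (the plan's value), the omitted variable correlates ρ = 0.3 to 0.5 with PAID, and it differs by 0.5 SD between completers and non-completers.

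- The completers' mean on that variable is off by 0.175 × 0.5 = 0.0875 SD.
- This shifts PAID by ρ × 0.0875, and conditioning on baseline PAID recovers half.
- Bias in one arm's week-24 mean: ρ × 0.0875 × (1 − 0.5) = 0.013 SD (ρ = 0.3) to 0.022 SD (ρ = 0.5).

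For the difference between arms:

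- same relation in both arms: the two biases cancel, giving about 0;
- relation in one arm only: 0.013 to 0.022 SD;
- opposite relations in the two arms: 0.026 to 0.044 SD.

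A large-sample simulation with these inputs agrees to within about 0.002 SD.

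A second simulation used N = 126, a covariate coefficient of 0.4, and a covariate unrelated to baseline PAID, so that baseline recovers nothing. Bias was nil with equal relations and about 0.06 SD with opposite relations. In the opposite case the pooled completer test picked the covariate only about 5% of the time, because the differences in the two arms offset each other.

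**The case against.** The best defence is that little harm follows. The variables missed most often are the weak predictors. Omitting one biases the comparison only if it predicts PAID beyond the PAID scores already modelled and its link with dropout differs between arms. Even then the bias in step 4 is small against the design effect of 0.5 SD. This stands, and it sets the weight of the point.

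Three stronger readings are tempting, and the documents do not support them.

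- *The rule misses real predictors about half the time.* That holds only near 0.46 SD, at an assumed 0.05 level. The plan gives neither figure, and the miss rate runs from 86% to 8% over 0.2 to 0.8 SD.
- *Adjustment happens only through this test.* Baseline PAID and demographic variables have other ways in, and section 3.9 says medication changes will be controlled for.
- *Testing many scales will flag some by chance and so do damage.* With ten independent null variables the chance of at least one flag is 1 − 0.95^10 = 40%. The count and the independence are assumptions, however, and adjusting for an irrelevant baseline variable does not bias a randomised comparison in a linear model. It costs about one degree of freedom.

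Two things are left after the defence. Dropout that differs by arm is plausible here: participation takes about 30 hours in the experimental arm and 5 in usual care (section 3.6.3), and the arms receive the tablet at different times (section 3.4). A pooled completer test is poorly suited to detect that case. The completers-only comparison does not fill the gap, since it rests on a stricter missingness assumption than the mixed model.

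**Conclusion.** The point holds in a limited form. For non-demographic baseline variables such as PHQ-9, PCL-5 and social support, entry into the primary model depends on a test that, with 22 against 104, misses 75% of real differences of 0.3 SD and 44% of those of 0.5 SD. Failure of that test is then read as evidence that dropout is unsystematic. These rates assume a two-sided 0.05 level and the planned 17.5% loss; they fall somewhat if intermittent missingness enlarges the incomplete group.

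The expected effect on the treatment estimate is about zero when dropout acts alike in both arms, and roughly 0.01 to 0.06 SD under the illustrative assumptions when it does not. A reader might infer that the primary estimate is seriously compromised; the calculations do not show that. This is a cheap improvement to the plan and does not threaten its conclusions.

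**What to change.** In the Missing Data paragraph, replace the test-then-adjust rule with a short pre-specified list of baseline variables already collected, for example PHQ-9, PCL-5, social support, HbA1c and age. Either:

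- enter them in the primary PAID model whatever their p-values, and state that they are exempt from the p < 0.05 retention rule in section 3.7.1, which could otherwise remove them again; or
- use them as auxiliary variables in multiple imputation.

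Keep screening PAID as the baseline outcome in the repeated-measures model and do not also add it as a covariate. It is the only PAID score before randomisation, so it would appear on both sides of the equation. Keep the completer v non-completer table, as description only.

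The cost is a change of wording and a few degrees of freedom. No new data are needed.
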